6.0 DRUG INFORMATION

Poly-ICLC is classified as an investigational new drug. It is a synthetic complex of polyinosinic and polycytidylc acid, stabilized with polylysine and carboxymethyl cellulose. The thermal denaturation point is 89.5° C, about 40° C above that of plain polyI-polyC; the resistance to hydrolysis is several times that of the parent compound, and it induces peak levels of about 5000 IU of interferon per ml of serum in monkeys given 2 mg/kg intravenously.

The current study will be done under IND #43984, held by Oncovir. The drug to be used in this study is prepared and packaged in the GMP facility of Bioserv, Inc, San Diego, under the direction and under contract to Oncovir. It is then tested for identity (RNAase resistance and thermal denaturation) bioactivity in primates, sterility and pyrogenicity before release for clinical experimental use.

FORMULATION: Supplied in 1 ml vials of 2 mg/ml opalescent solution

STORAGE: Should be refrigerated but NOT FROZEN. Stable at room temperature for 3 days.

SOLUTION PREPARATION: Solution is injected as supplied.

ADMINISTRATION: Administered as a single intramuscular injection twice per week.

SIDE EFFECTS: Discomfort at injection site, occasional malaise, myalgias, or fever. Rare transient leukopenia has been reported. At higher intravenous doses, transient liver enzyme and BUN elevations, and leukopenia have been reported. Idiosyncratic hypercoagulopathy has been reported in dogs at very high doses but has not been seen in humans.

MAXIMAL TOLERATED DOSE: As reported in cancer trials, 250-300 micrograms/kg.

The drug will be obtained from Oncovir.

To obtain drug, call:

[name]
Oncovir, Inc
[name]
Washington, DC, 20008
[contact]
[contact]
Email: [contact]; [contact]

Drug Accountability:

The research pharmacist at each participating site will maintain records of all dispensed vials of study drugs. All unused vials will be returned to the manufacturer (Oncovir) at the completion of the study as well as all the drug accountability forms. A copy of these records will be kept in the study binder at the coordinating site.

7.0 RESPONSE CRITERIA

MRI Response Criteria: Comparison of objective assessments are based on major changes in tumor size compared to the baseline scan. Determination of progressive disease is based on tumor measurements described below.

Interpretation of anatomic (MRI) response rates in gliomas can be difficult. Tumors may be non-enhancing, and certain area of enhancement may represent post-operative or radiation change. Shrinkage of enhancing lesions can also be seen for months after radiation alone. These factors may confound the MRI interpretation of tumor response to poly-ICLC. Also in the Principal investigator's previous experience, tumor regression or stabilization on MRI was seen at 12 and 52 months in some patients on poly ICLC. Hence in the absence of clearly progressive disease (worsening neurological status, significant increase in tumor size on MRI), poly-ICLC should be continued for possible late benefits.

7.1 EVALUATION CRITERIA

7.1.1 Methodology to Determine Tumor Measurement

All measureable tumors will be measured at each evaluation and will be used in the response assessment.

Measurable Disease: Bi-dimensionally measurable lesions with clearly defined margins by MRI or CT scan.

Evaluable Disease: Uni-dimensionally measurable lesions, masses with margins not clearly defined.

Non-Evaluable Disease: Not Applicable for response evaluation

For all measurable tumors, the 3 dimensional measurements: width (W), transverse (T), and length (L) measurements need to be recorded (if length L can be measured), using either T1 or T2 MR weighted images (which ever gives the best estimate of tumor size). The following section describes the methodology.

1. Longest diameter of the tumor should be selected in the axial plane or the plane in which the tumor is best seen or measured, provided the same plane is used in follow ups.
2. The longest measurement of the tumor (or width, W) should be determined.
3. The 2 perpendicular measurements should be determined (transverse (T) measurement-perpendicular to the width in the selected plane, and the length (L) – tumor extent in the plane perpendicular to the selected plane).

The primary tumor response rate endpoint will be based on the 2 dimensional measurements (TxW) as in modified MacDonald criteria (section 7.1.2), which, in addition to radiographic scans, comprise elements of the steroid use. The response rate based on the 3 dimensional measurements (TxWxL) will be a secondary endpoint (section 7.1.3).

All lesions are to be measured at each evaluation; however, if there are too many measurable lesions to measure at each evaluation (i.e. more than 10), choose the largest two to be followed before a subject is entered on study. The remaining lesions will be considered evaluable for the purpose of objective status determination.

7.1.2 Tumor Response Criteria on 2 Dimensional Measurements (per Modified MacDonald Criteria)

- a. Complete Response (CR): Complete disappearance of all measurable and evaluable disease. There are no new lesions and no evidence of non-evaluable disease. All measurable, evaluable and non-evaluable lesions and sites must be assessed using the same techniques as baseline. Patients must not be on any steroids.
- b. Partial Response (PR): $\geq 50\%$ decrease over baseline in the sum of products of perpendicular diameters of all measurable lesions. There is no progression of evaluable disease and no new lesions. All measurable and evaluable lesions and sites must be assessed using the same techniques as baseline. The steroid dose at the time of the scan should be no greater than the maximum dose during the first 8 weeks since initiation of therapy.
- c. Stable Disease (SD): Does not qualify for CR, PR, or progression. All measurable and evaluable sites must be assessed using the same techniques as baseline. The steroid dose at the time of the scan should be no greater than the maximum dose used during the first 8 weeks since initiation of therapy.
- d. Progressive Disease (PD): $\geq 25\%$ increase in the sum of products of all measurable lesions over baseline using the same techniques as baseline, **or** clear worsening of any evaluable disease, **or** appearance of any new lesion/site, **or** clear clinical worsening **or** failure to return for evaluation due to death or deteriorating condition (unless clearly unrelated to this cancer).

7.1.3 Tumor Response Criteria Based on 3 Dimensional Measurements

- a. Complete Response (CR): Disappearance of all measurable and evaluable tumors. There are no new lesions and no evidence of non-evaluable disease.
- b. Partial Response (PR): $> 65\%$ decrease in the sum of the products of the three perpendicular diameters of the measurable tumors relative to the sum of products of initial baseline measurements - $LxWxT$ (current scan) $< 0.65 * LxWxT$ (initial scan). There is no progression of evaluable disease and no new lesions.
- c. Stable disease (SD): Neither sufficient decrease in the product of the three perpendicular diameters to qualify for partial response nor sufficient increase to qualify for progressive disease.
- d. Progressive Disease (PD): $>25\%$ increase in the sum of products of the three perpendicular diameters of the measurable tumors relative to the initial baseline measurement - $LxWxT$ (current scan) $> 1.25 * LxWxT$ (initial

scan) **or** the development of any new sites of disease. As post-radiation changes are often seen on post-treatment imaging studies, classification of a patient as having progressive disease may require several serial MRIs.

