3.2.3 Criteria

Subjects must have demonstrated either tumor progression or recurrence by any of the radiographic criteria and/or clinical criteria as defined below:

- a. Subjects with progressive non-resectable disease regardless of location in the brain or spine are eligible for this study. Patients with evidence of leptomeningeal dissemination are eligible for this study. Patients do not require biopsy/histologic confirmation at the time of progression or relapse.
- b. Radiographic progression is defined as >40% increase in the product of the three perpendicular diameters of current tumor relative to the baseline measurement (defined as either the initial scan or scan at start of a previous therapy):
length (L) x width (W) x transverse (T) (current scan) $> 1.4 \times L \times W \times T$ (baseline scan), or the development of any new sites of disease independent of the response of the initial tumor.
See section 7.1.2 for methodology for tumor measurement.
- c. Post radiation changes are often seen on post-treatment imaging studies, so that classification of a patient as having progressive disease may require several serial MRI's if the child has received radiation within the preceding 12 months.
- d. Tumor volume includes the entire tumor volume seen on gadolinium enhanced T1 MR imaging plus non-enhancing abnormality seen on T2 or FLAIR. Coronal and axial images will be evaluated.
- e. All tumor cysts will be included in the tumor volume
- f. Clinical progression without radiographic progression includes children with optic pathway gliomas who demonstrate sustained decrease in visual fields and/or acuity in three serial vision examinations. Each of the vision examinations must be performed >2 weeks apart.
- g. Children with previously negative cerebrospinal fluid (CSF) cytology who show evidence of tumor cells in fluid obtained by lumbar puncture can be designated as having progressive disease in the absence of radiographic evidence of progression.

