7.1.4 Response Assessment

Tumor response will be assessed at 3, 6, 9, 12, 18, 24 months after starting the therapy, as well as at the time of going off study if prematurely. The overall response rate (ORR), defined as the percent of evaluable subjects who experience a complete response or partial response or stable disease, will be determined. The primary endpoint will be progression free survival rate (per MacDonald Criteria) at 6 months after starting therapy. Secondary endpoints also include tumor ORR at 6 months and 2 years after starting therapy and also the duration of the 'good' response. The traditional overall response rate (CR's and PR's only) will also be summarized.

Each subject will be classified according to their "best response" for the purposes of analysis of treatment effect. Best response is determined from the sequence of the objective statuses described above.

Any subject removed from study protocol because of unacceptable progression (see Section 8.1) will be counted as progressive disease in the efficacy analysis.

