8.0 CRITERIA FOR REMOVAL FROM PROTOCOL THERAPY AND OFF STUDY CRITERIA

8.1 Criteria for Removal from Protocol Therapy

a. Progressive disease

Note: Transient enlargement of enhancing disease with subsequent shrinkage has been reported during poly-ICLC treatment. Because of this, if the patient has progressive disease by the conventional definition above but does not have unacceptable progression by the definitions below, the treating physician and patient have the options of continuing poly-ICLC treatment on this protocol or of discontinuing treatment.

b. Criteria for unacceptable progression: See definitions of tumor progression outlined in section 7.1.3

1. >50% increase in the product of the three perpendicular diameters of initial tumor relative to the initial baseline measurement – LxWxT (current can) $> 1.5 \times$ LxWxT (initial scan), or the development of any new sites of disease independent of the response of the initial tumor. Post radiation changes are often seen on post-treatment imaging studies, so that classification of a patient as having progressive disease may require several serial MRI's if the child has received radiation within the preceding 12 months.

2. Unacceptable worsening of neurological symptoms that cannot be controlled with corticosteroids.

3. Any other radiological or clinical evidence of worsening to the extent that the treating physician feels it is not in the patient's best interest to continue poly-ICLC.

c. Physician determines it is in patient's best interest.

- d. Patient and/or parent/guardian refusal to continue or inability to comply with protocol
- e. Grade 3 or 4 toxicity that does not resolve to Grade 1 within three weeks after interruption of therapy, or recurrent grade 3 or 4 toxicity at a reduced dose level (see section 4.2).

Note: If final analysis confirms a beneficial effect of poly-ICLC, and/or if tumor recurs after withdrawal from poly-ICLC at the end of the 2-year prescribed treatment period, participating subjects may be offered continued treatment with poly-ICLC (subject to drug availability at that time).

- f. Completion of planned therapy.

Subjects who are off protocol therapy are to be followed until they meet the criteria for Off Study (see below). Follow-up data will be required, unless consent is withdrawn, every 3 months for the first year, every 4 months for the second year, every 6 months for the third year, and then yearly thereafter

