9.1.6 Accrual and study duration

All the 23 patients are expected to be accrued in 3 years and the total study duration will be about 5 to 5.5 years.

9.2: Analysis of Results

9.2.1: Analysis of anti-tumor activity

The "best response" rate is defined as the percent of evaluable subjects who experience a CR or PR or SD (see Section 7.1.2). The best response rates as well as overall response rates at 6 and 24 months will be estimated and exact lower one sided confidence intervals for the true response rates will be presented (Jung, 2004). The duration of response for each subject that has tumor response will be summarized in a table. The same analysis will be done for the tumor response rate based on 3 dimension measurements as in section 7.1.3.

9.2.2: Summary of toxicities and side effects

All observed toxicities and side effects will be recorded on toxicity sheets and the data collection forms. Toxicity information including type, severity, time of onset and resolution, and probable association with the study drugs will be recorded. Toxicities will also be analyzed by NF1 status (NF1 vs. non NF1 subject cohorts). Tables will be constructed to summarize the observed incidence by type of toxicity and severity.

9.2.3: Analysis of Survival

Overall survival and progression-free survival rates will be estimated using the Kaplan-Meier method (Kaplan, 1958).

9.2.4: Analysis of biochemical measures.

Laboratory studies will be done on subject's serum and peripheral blood drawn prior to and at two weeks after starting treatment with Poly ICLC. Levels and changes in the measurement of serum markers and proteins such as OAS, interferon α , β , γ , PKR kinase, eIF2a, and p21^{Waf-1} will be determined via proteomic analysis. For each marker, a Fisher's exact test or a Wilcoxon rank sum test will be used to assess the association of a baseline protein level or changes from baseline against tumor response status at 6 months. A log rank test will be used if the outcome is progression free survival.

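### The 3D partial-response rule in 7.1.3b sets two different cut-offs: a >65% decrease in words, but only a >35% decrease in the formula

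*Combined protocol and SAP*

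**What the plan says.** Section 7.1.3b states the 3D PR threshold twice in one sentence. In words, the threshold is more than 65%, and it applies to the "decrease in the sum of the products of the three perpendicular diameters of the measurable tumors relative to the sum of products of initial baseline". As a formula, it is "current scan) $< 0.65 * LxWxT$ (initial scan". PR also requires no new lesions and no progression of evaluable disease. Under 7.1.3c, stable disease (SD) is whatever is neither PR nor progression (PD).

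Section 7.1.4 has two response rates. The overall response rate (ORR) is "defined as the percent of evaluable subjects who experience a complete response or partial response or stable disease". In addition, "The traditional overall response rate (CR's and PR's only) will also be summarized". Section 9.2.1 defines the best response rate as CR, PR or SD, and then says of the antitumour analysis: "The same analysis will be done for the tumor response rate based on 3 dimension measurements as in section 7.1.3".

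The protocol has three other rules on the three-diameter product, each with a percentage and a multiplier:

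- 3.2.3b (entry): more than 40% "increase in the product of the three perpendicular diameters of current tumor relative to the baseline measurement", with multiplier 1.4.
- 7.1.3d (3D progression): more than 25% increase, with multiplier 1.25.
- 8.1b (unacceptable progression): more than 50% "increase in the product of the three perpendicular diameters of initial tumor relative to the initial baseline measurement", with multiplier 1.5.

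**The concern.** For a decrease, the multiplier should be the fraction of tumour remaining. The formula appears to carry the percentage lost instead. If so, two readers who follow the same sentence could classify identical measurements differently, one as SD and the other as PR.

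Tumour response on 3D measurements is a named secondary endpoint (objective 1.2.1, 7.1.1, 9.0 and 9.2.1). At stake are the PR/SD split of 3D best response and any CR+PR rate on 3D measurements. Following the formula makes both look more favourable than the worded rule allows.

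**Working it through.** **Inputs.** The cut-offs are from 3.2.3b, 7.1.2, 7.1.3 and 8.1b. Sample sizes of 14 (stage 1) and 23 (total) are from 9.1.1. Let r = LxWxT (current) / LxWxT (baseline), using sums of products where there are several lesions.

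**Step 1: the protocol's own words and multipliers.** Increase of x%: r > 1 + x/100. Decrease of x%: r < 1 − x/100.

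| Rule | Words | Multiplier implied | Multiplier printed |
|---|---|---|---|
| 7.1.3d | >25% increase | 1 + 0.25 = 1.25 | 1.25 |
| 3.2.3b | >40% increase | 1 + 0.40 = 1.40 | 1.4 |
| 8.1b | >50% increase | 1 + 0.50 = 1.50 | 1.5 |
| 7.1.3b | >65% decrease | 1 − 0.65 = 0.35 | 0.65 |

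The three increase rules reproduce. The one decrease rule does not: r < 0.65 means a decrease of more than 1 − 0.65 = 35%.

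**Step 2: which subjects change category.** This assumes no new lesion and no progression of evaluable disease.

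| r | By the words | By the formula | Counted in ORR |
|---|---|---|---|
| 0.30 | PR | PR | yes, both |
| 0.36, 0.50, 0.64 | SD | PR | yes, both |
| 0.66, 1.00 | SD | SD | yes, both |
| 1.26 | PD | PD | no, both |

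The disputed band is 0.35 ≤ r < 0.65. A move between SD and PR leaves CR+PR+SD unchanged, so the 3D ORR and the best response rate are the same under both readings.

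**Step 3: a worked case.** A tumour shrinks from 40 x 30 x 30 mm to 32 x 24 x 24 mm.

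- Volume ratio: 18,432 / 36,000 = 0.512.
- Area ratio: (32 x 24) / (40 x 30) = 768 / 1,200 = 0.64, a 36% decrease.
- Result: SD by the 2D rule (which needs at least 50%), SD by the 3D words, PR by the 3D formula.

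**Step 4: size.** Each subject in the band moves a 3D CR+PR rate by 1/n.

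- n = 23: 1/23 = 4.3 points; 2/23 = 8.7; 3/23 = 13.0; 5/23 = 21.7.
- n = 14 (stop at stage 1): 1/14 = 7.1 points.

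The number of subjects in the band is an assumption; the documents give none.

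**Step 5: which half is likely to be the slip.** If all three diameters shrink in proportion, 3D ratio = (2D ratio)^1.5.

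- The 2D PR cut-off of a 50% decrease converts to 0.5^1.5 = 0.354, a 64.6% decrease. This matches the words.
- A 3D ratio of 0.65 is 0.65^(1/3) = 0.866 per diameter. The area ratio is then 0.866^2 = 0.750, a 25% decrease and half of what the 2D rule asks.
- The progression cut-offs are not converted in this way: 1.25^1.5 = 1.40, yet 7.1.3d keeps 1.25. The scaling therefore supports 0.35 but does not prove it.

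**Step 6: the primary analysis.** PFS6 is assessed by 7.1.2. An exact binomial calculation of the two-stage rule (stop at ≤7 of 14, reject the therapy at ≤15 of 23) gives alpha 0.046, power 0.802 at 75% and early stopping 0.605 under the null, against the plan's 5%, 80% and 61%. No 3D threshold enters it.

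**The case against.** The best case against making much of this concerns impact, since the contradiction is plain on the page.

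- **No 3D CR+PR table is named.** Section 7.1.4 promises the traditional rate without mentioning 3D. The 9.2.1 sentence that extends the analysis to 3D follows rates that count SD. This stands as a qualification. A 3D CR+PR rate is a fair reading, because 7.1.4 follows both sets of criteria and 9.0 lists 3D response rates as secondary, but it is still a reading. The 3D PR/SD split is affected either way.
- **No decision depends on it.** 3D results are secondary, and no test or threshold is attached to them. This is correct and limits the severity.
- **The denominator may be below 23.** Rates use evaluable subjects, and length is recorded only where it can be measured. This also stands; only 1/n per subject is firm.
- **Being in the band is not sufficient for PR.** A subject with a new lesion or evaluable progression is not PR under either reading. True, and such a subject moves nothing.
- **Duration may be unaffected.** Section 9.2.1 says "The duration of response for each subject that has tumor response will be summarized in a table" without limiting response to CR and PR, and the context leans towards including SD. Duration is therefore touched only if response there means CR or PR. That is a separate ambiguity, and this correction does not depend on settling it.

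**Conclusion.** The concern holds. Section 7.1.3b contains two incompatible cut-offs, r < 0.35 and r < 0.65, and no other section resolves them. The formula is probably the slip: the words say 65%, the other three multipliers agree with their words, and the 2D rule points to 0.354 under proportional shrinkage. The intended cut-off is still the sponsor's to confirm.

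The effect is 4.3 points on a 3D CR+PR rate per reclassified subject at n = 23 (7.1 at n = 14). The range of 4.3 to 21.7 points rests wholly on the assumption of 1 to 5 such subjects among 23 evaluable. The error is confined to a secondary, descriptive result, so it should be fixed but does not threaten the trial's main conclusion.

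**What to change.** Ask the sponsor to confirm that the intended 3D PR threshold is a decrease of more than 65%. If so, change the multiplier in 7.1.3b from 0.65 to 0.35. If the formula was intended, change the words to a decrease of more than 35% instead. Settle this before the 3D results are analysed, so that the cut-off is not chosen with the data in view, and re-derive any 3D PR classification already made.

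The cost is one number in the protocol. Reclassification uses the width, transverse and length measurements that 7.1.1 already requires (where length could be measured), so no new data are needed. The design, sample size and primary analysis stay as they are.

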1.2 Secondary Objectives

- 1.2.1 To determine the overall response rate to poly-ICLC in the treatment of children with recurrent low grade gliomas; tumor assessments are to be performed per 3D measurements.
- 1.2.2 Progression free survival over the course of the study.
- 1.2.3 Overall survival at 6 months – the time from starting study therapy to death from any cause.
- 1.2.4 To assess the toxicity associated with treatment with poly-ICLC in pediatric patients with recurrent low grade gliomas.
- 1.2.5 To study the effect of treatment with poly-ICLC on the signaling pathways controlling apoptosis in low grade glioma tumor cells.
- 1.2.6 To determine if surrogate markers of tumor response and progression can be identified in the serum, PBMC and/or cerebrospinal fluid of patients with recurrent low grade gliomas treated with poly-ICLC. Proteomics analysis will be performed to obtain protein levels of these markers such as OAS, interferon α , β , γ , PKR kinase, phosphorylation state of eIF2a, and induction of p21^{waf-1}.

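### Clear worsening of evaluable disease is not progression under the 3D criteria, so a child with measurable disease who stays on treatment can count as a 3D responder

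*Combined protocol and SAP*

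**What the plan says.** The protocol has two sets of response criteria. The 2D set (7.1.2) serves the primary endpoint, progression-free survival at 6 months (PFS6). The 3D set (7.1.3) is secondary, but it is the basis named for the first secondary objective, the overall response rate (ORR): in 1.2.1, "tumor assessments are to be performed per 3D measurements".

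- **2D progression (7.1.2d).** Besides growth of measurable lesions and new lesions, it includes "clear worsening of any evaluable disease", "clear clinical worsening" and "failure to return for evaluation due to death or deteriorating condition". 2D stable disease (SD) is whatever is not CR, PR or progression.
- **3D progression (7.1.3d).** It has two grounds: an increase above 25% in the summed product of the three diameters of the measurable tumors, or "the development of any new sites of disease".
- **3D stable disease (7.1.3c).** It is defined on size only: "Neither sufficient decrease in the product of the three perpendicular diameters to qualify for partial response nor sufficient increase to qualify for progressive disease".
- **3D CR and PR (7.1.3a, b).** CR needs evaluable tumors to have gone. PR is barred if evaluable disease has progressed.
- **Many lesions (7.1.1).** With more than 10 measurable lesions, the largest two are followed. Of the others: "The remaining lesions will be considered evaluable for the purpose of objective status determination".
- **ORR (7.1.4).** It is "the percent of evaluable subjects who experience a complete response or partial response or stable disease". Section 9.2.1 defines the best response rate in the same way and repeats the analysis for 3D.

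Two provisions limit the effect. Section 7.1.4 counts a subject removed for unacceptable progression (8.1b) as progressive disease in the efficacy analysis. Section 9.1.5 counts an endpoint that cannot be assessed against the therapy.

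**The concern.** Evaluable disease counts in the 3D set when a response is being denied, but not when progression is being declared. Because the ORR treats stable disease as success, a worsening that is not progression becomes a response. The same child at the same visit can then be a progression event for PFS6 and a success in the 3D ORR.

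The result at stake is the 3D ORR at 6 months and 2 years, with the 3D best response rate and duration of response. In a rate that includes stable disease, the line between stable and progressive disease decides who counts. An error on that line which can only raise the rate flatters the treatment in a single-arm trial with no control group to share it.

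**Working it through.** **The plan's own figures.** The only design calculation concerns PFS6: 14 subjects, stop if 7 or fewer succeed, otherwise 23 subjects, success if 16 or more. Exact binomial calculation gives power 0.802 at 75% (stated 80%), attained alpha 0.046 (stated 5%) and early stopping probability 0.605 under the null (stated 61%). These figures use the 2D criteria, and the present point does not depend on them. The plan states no figure for the 3D ORR.

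**Grounds for progression side by side.**

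| Ground | 2D (7.1.2d) | 3D (7.1.3d) |
|---|---|---|
| Growth of measurable tumors | yes, 25% or more in area | yes, above 25% in product |
| New lesion or site | yes | yes |
| Worsening of evaluable disease | yes | no |
| Clinical worsening | yes | no |
| No return because of death or deterioration | yes | no (see 9.1.5) |

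**Cases taken through 7.1.3 as written.**

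1. *Measurable tumor with product up 10%, no new site, evaluable disease clearly worse.* Not CR, not PR and not PD. The change in product is neither a sufficient decrease nor a sufficient increase, so 7.1.3c makes the child SD, and 7.1.4 makes SD a success. In 2D the same child is PD.
2. *Eleven measurable lesions.* Two are followed and 11 − 2 = 9 become evaluable. Growth in any of the nine is PD in 2D and cannot be PD in 3D.
3. *Product falls enough for PR, but evaluable disease progresses.* PR is barred by 7.1.3b. PD is not met. SD is not met either, because the decrease is sufficient. The child has no 3D class.
4. *Evaluable disease only.* Under 7.1.1 this means lesions measurable in one dimension or with unclear margins, so there may be no product of three diameters. The class is unclear, and the child may be unfavourable under 9.1.5 or outside the evaluable denominator.

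**Which of these children are caught elsewhere.** A child in case 1 or 2 who is removed for unacceptable progression is counted as PD under 7.1.4. Section 9.1.5 does not help for the others, because their scan exists and yields a class. The note under 8.1a allows treatment to continue after conventional progression that is not unacceptable, so children who worsen and stay on treatment are foreseen by the plan.

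**Size.** With N = 23 (9.1), all evaluable, each child moved from PD to SD changes the 3D ORR by 1/23 = 0.043, or 4.3 points. The number k of such children is not in the documents. Purely for illustration, take a correctly classified rate of 16/23. The bounds are one-sided 95% Clopper-Pearson limits, which ignore the two-stage design:

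| k | 3D ORR | Lower bound |
|---|---|---|
| 0 | 16/23 = 69.6% | 50.4% |
| 1 | 17/23 = 73.9% | 54.9% |
| 2 | 18/23 = 78.3% | 59.6% |
| 3 | 19/23 = 82.6% | 64.5% |

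The best response rate moves only for a child with no earlier visit at SD or better, since such a visit already counts as success. The CR+PR rate does not move, because none of these children is CR or PR under either reading. PFS6 uses 7.1.2 and does not move.

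**The case against.** The strongest reply is that the 3D measure is meant to be volumetric. Section 7.1.1 presents the 2D criteria as going beyond the scans and the 3D rate as resting on three measurements. A secondary endpoint of that kind may legitimately leave clinical worsening out. That stands for clinical worsening, where the plan need only state its intention. It does not stand for evaluable disease, which is an imaging finding and which 7.1.3a and b already use.

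A reader might infer more than the documents support:

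- *That every child with evaluable or clinical worsening is a 3D responder.* Section 7.1.4 applies to the efficacy analysis without restriction to 2D. Section 8.1b covers neurological worsening not controlled with corticosteroids, and other radiological or clinical worsening that the physician judges sufficient. Failure to return is in substance covered by 9.1.5. The gap is limited to worsening that does not lead to removal for unacceptable progression.
- *That children with diffuse or leptomeningeal disease are almost certain 3D responders.* Case 4 shows that their class is unclear, and such disease may also progress through new sites, which 7.1.3d counts.
- *That the bias is 5 to 10 points.* This needs an assumed 10–20% of progressions at a 50% progression rate (0.50 × 0.10 to 0.50 × 0.20), and the documents give no basis for that share. The 3D size ground is also the lower bar: under equal growth in all directions, 25% in area is 1.25^1.5 − 1 = 40% in volume. Some of these children will therefore already be 3D PD by size.
- *That a planned comparison of 2D with 3D is confounded.* No such comparison is specified. Section 9.2.1 reports response rates under both sets.

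**Conclusion.** The point holds for evaluable disease. Followed as written, 7.1.3c and d class a child with measurable disease and clear evaluable worsening as stable, and 7.1.4 then counts that child as a 3D success, unless there is removal for unacceptable progression or no assessable endpoint. PR-size shrinkage with evaluable progression has no class. This is a rule that gives a wrong result, not only a missing detail.

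The size is 4.3 points per child at 23 evaluable subjects, always upward. The total cannot be computed from the documents, and the table under the check is an illustration. The effect is confined to secondary 3D results. PFS6, the stopping rule and the CR+PR rate do not change. The omission of clinical worsening is an open question of intent and is not shown to be an error.

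**What to change.** For response classification in the analysis only:

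1. Add to 7.1.3d the 2D ground "clear worsening of any evaluable disease". This also gives case 3 a class.
2. Redefine 7.1.3c as any assessed status that does not qualify for CR, PR or PD.
3. State that the 7.1.4 rule on removal for unacceptable progression applies to the 3D ORR.
4. State whether clinical worsening is deliberately excluded from 3D PD.

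Section 8.1b refers to 7.1.3 for its definitions of tumor progression. The sponsor must reconcile those passages so that a change made for the analysis does not alter the criteria for removal from treatment.

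The cost is wording. Evaluable disease is already assessed for the 2D criteria, so no new data are needed. The downside is a slightly lower 3D ORR. The two sets would still differ in their steroid conditions and in the serial-MRI allowance of 7.1.3d, so the change does not make them identical apart from size.
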